5.2 Application to Malignant or Pre-malignant Skin Conditions

The use of ELIDEL Cream, 1% should be avoided on malignant or pre-malignant skin conditions. Malignant or pre-malignant skin conditions, such as cutaneous T-cell lymphoma (CTCL), can present as dermatitis.

ELIDEL Cream, 1% should not be used in patients with Netherton's Syndrome or other skin diseases where there is the potential for increased systemic absorption of pimecrolimus. The safety of ELIDEL Cream, 1% has not been established in patients with generalized erythroderma.

The use of ELIDEL Cream, 1% may cause local symptoms such as skin burning (burning sensation, stinging, soreness) or pruritus. Localized symptoms are most common during the first few days of ELIDEL Cream, 1% application and typically improve as the lesions of atopic dermatitis resolve [see Adverse Reactions (6.1)].

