I have read this protocol and I agree to conduct the study as described, in compliance with Good Clinical Practice (ICH E6), the Declaration of Helsinki (Fortaleza, Brazil, October 2013) and the rules and regulations.

[name] [name] (Oct 21, 2016)

Date:

Signature of CRO Biostatistician
[name]
Printed Name:
Oct 21, 2016

CONFIDENTIAL

Version 2.0 Dated 14 Oct 2016

STUDY SYNOPSIS

Study Title	A Randomized, Prospective, Multicenter, Double Blind, Parallel				
Study Title					
	Assignment, Placebo Controlled Bioequivalence Study of Pimecrolimus Cream, 1% and Elidel [®] (Pimecrolimus) Cream, 1% in Patients with				
	Mild to Moderate Atopic Dermatitis				
Study Design	Randomized, prospective, multicenter, double blind, parallel				
	assignment, placebo controlled therapeutic equivalence study				
Sample Size	648 Subjects				
Protocol Number	CD-14-875				
Study Center	Multi-center study				
Study Type	Bioequivalence study with clinical endpoints				
Sponsor	DPT Laboratories, Ltd., an affiliate of Mylan Inc.				
	[name]				
Investigational	Test drug: Pimecrolimus Cream, 1%				
Products & Study	Reference listed drug (RLD): Elidel® (Pimecrolimus) Cream 1%				
Arms	Placebo: Vehicle cream				
Dosage of	A thin layer is to be applied to all affected skin areas twice daily for 2				
Investigational	weeks (14 days)				
Product					
Objectives	Primary Objective:				
	• To establish the bioequivalence between test and reference listed				
	drugs using the primary endpoint in the Per Protocol population				
	Additional:				
	• To establish superiority of the each treatment over the placebo using the primary endpoint in the modified intent to treat (mITT) population and				
	Last Observation Carried Forward (LOCF)				
	• To assess individual signs and symptoms of Atopic Dermatitis (i.e., erythema, induration/papulation, lichenification and pruritus) in each				
	treatment group To compare the sofety and tolerability between the test and reference				
	To compare the safety and tolerability between the test and reference drugs				
Study Population	Non-immunocompromised males and females with mild to moderate				
	atopic dermatitis who have failed to respond adequately to other topical				
	prescription treatments, or when those treatments are not advisable.				
	Age: 8 years and above				

CONFIDENTIAL

Version 2.0 Dated 14 Oct 2016

Patient Selection

Screening Criteria:

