3.1.1.8 Investigator's Global Assessment (IGA)

At each visit, the investigator will assess the overall status of the subject's skin for AD using the IGA as per the scale noted in Appendix III. The IGA is a static assessment of how the subject's overall skin is observed at the time of the current visit. Scores or severity from prior visits should not be considered. The IGA scores for each visit will be documented on the source and the Case Report Form. Subjects must have a score of mild to moderate AD on IGA in order to be enrolled in the study.

- 3.1.1.9 **Pruritus Assessment**: Pruritus will be assessed by questioning the subject or the subject's guardian regarding the intensity of overall itching/scratching/discomfort in the 24 hours prior to the visit using the scale mentioned in Appendix II.
- 3.1.1.10 **Local Application Site Reactions**: Subjects will also be assessed at screening for evaluation of pre-treatment local application site reactions. At each study visit, the investigator will evaluate any application site reactions with separate severity scores for dryness, burning/stinging, erosion, edema, and pain. At each visit the reactions will be

CONFIDENTIAL

Version 2.0 Dated 14 Oct 2016

noted and classified as mild, moderate or severe. Refer to Appendix IV Local Irritation Scale (LIS) for scoring of application site reactions.

- 3.1.1.11 **Physical Examination**: Subjects will undergo a general physical examination. A detailed dermatological examination is required. A full body dermatologic examination will assess if the subject has any dermatologic malignancies. If the subject does have a dermatologic malignancy, they should not be enrolled. The following systems should also be evaluated: head, ears, nose, throat, eyes, central nervous system, respiratory, cardiovascular, gastrointestinal, and musculoskeletal.
- 3.1.1.12 **Concomitant Medication:** History concomitant medications used will be obtained for at least the past 30 days. The start and stop date of medication use will be collected in addition to the reason for use. See section 6.3.

3.1.1.13 Screening Criteria:

Subjects will be evaluated to confirm that they meet the following screening criteria.

- Non-immunocompromised male or female aged 8 years and older
- Clinical diagnosis of mild to moderate atopic dermatitis (AD), as defined by the criteria of Hanifin and Rajka

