3.1.2 V2 - Baseline and Randomization Visit (Day 1)

The study specific procedures to be evaluated at baseline visit are:

- 3.1.2.1 Vital signs (See section 3.1.1.4)
- 3.1.2.2 Signs and symptoms evaluation (See section 3.1.1.6)
- 3.1.2.3 Body surface area assessment (See section 3.1.1.7)
- 3.1.2.4 Investigator's Global Assessment (IGA) (See section 3.1.1.8)
- 3.1.2.5 Pruritus Assessment (See section 3.1.1.9.)
- 3.1.2.6 Local application site reactions (pre-treatment) (See section 3.1.1.10)
- 3.1.2.7 **Urine pregnancy test** will be conducted for female subjects of child bearing age prior to dosing.
- 3.1.2.8 **Adverse Event Assessment**: Subjects will be questioned regarding adverse events in the form of non-leading questions (e.g., "How are you feeling?"). All adverse events will be assessed and documented and will be managed as per standard of care.
- 3.1.2.9 Concomitant medication (See section 3.1.1.12)
- 3.1.2.10 **Bland emollient collection:** Subjects will return with the bland emollient used over the past 7 days. The site staff will collect such as the subject should not use it while being treated with the study treatment.
- 3.1.2.11 Inclusion / Exclusion Criteria Evaluation (See section 4.1.)
- 3.1.2.12 **Randomization:** Subjects fulfilling inclusion and exclusion criteria will receive study product from the next available sequential randomized kit which contains one of the following three treatment arms:
 - > Test drug: Pimecrolimus Cream. 1%
 - ➤ Reference listed drug: Elidel® (Pimecrolimus) Cream 1%
 - ➤ Placebo: Vehicle of the test drug cream without Pimecrolimus

Each study product kit will contain three 100 gram tubes of study cream from the same randomized treatment arm. The kits will be packaged in a block size of 6. Each block will contain 2 kits of each treatment arm (2:2:2).

3.1.2.13 **Study Drug Dispensing:** Study drug tube(s) will be dispensed to each subject by a staff member delegated by the PI. The study drug dispenser will not participate in any clinical assessments. The delegated staff member will tear off the perforated label prior to dispensing to the subject. The perforated portion of the label contains the blinded treatment arm underneath an occlusive layer. The perforated label with blinded code will remain at the clinic site in case of emergency. (See section 6.5 regarding emergency unblinding.) The delegated staff member will dispense at least one tube of study cream.

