Subjects (or guardians) will be instructed to apply a thin layer to the affected areas twice daily for 2 weeks (14 days). Subjects/guardians will be instructed about the following: When applying assigned study treatment after a bath or shower, the skin should be dry. Caregivers applying study treatment to a subject, or subject who is not

CONFIDENTIAL

Protocol Number: CD-14-875 Version 2.0

Dated 14 Oct 2016

treating their hands should wash their hands with soap and water after applying study treatment. Caregivers who are pregnant, breastfeeding or may become pregnant should consult their physicians and follow their recommendations relating to the potential exposure to Pimecrolimus 1% Cream. Appendix V Instructions for the Patients will be reviewed with the subject or guardian.

The subject will be instructed to return all tubes to the study clinic.

3.1.2.14 **Diary Card Instructions / Schedule Next Visit**: Subjects or their guardians will be issued a diary card with instructions to record all applied and missed doses.

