4.1.2 Exclusion Criteria

- a) Females who are pregnant, breast feeding, or who wish to become pregnant during the study period
- b) Active cutaneous bacterial or viral infection in any treatment area at baseline (e.g., clinically infected atopic dermatitis, impetigo).
- c) Sunburn, extensive scarring or pigmented lesion(s) in any treatment area at baseline, which would interfere with evaluations
- d) History or presence of confounding skin conditions, e.g., psoriasis, rosacea, erythroderma, ichthyosis, or scabies.
- e) History or presence of Netherton's Syndrome, immunological deficiencies or diseases, HIV, diabetes, malignancy, serious active or recurrent infection, clinically significant severe renal insufficiency or severe hepatic disorders
- f) Concurrent disease or treatment likely to interfere with the study treatment or evaluations
- g) Use within one month prior to baseline of
 - ➤ Oral or intravenous corticosteroids (Subjects on stable and continued doses of nasal, or inhaled corticosteroids for conditions other than atopic dermatitis may be enrolled at the investigator's discretion when the investigator considers that such will not affect the efficacy or safety evaluations of the study. Ophthalmic corticosteroids are not excluded.)
 - ➤ UVA/UVB therapy
 - > PUVA (psoralen plus ultraviolet A) therapy
 - > Tanning booths
 - ➤ Nonprescription UV light sources
 - > Immunomodulators or immunosuppressive therapies
 - > Interferon
 - > Cytotoxic drugs
 - > Tacrolimus
 - > Pimecrolimus
- h) Use within 14 days of baseline of
 - > Systemic antibiotics
 - ➤ Calcipotriene or other vitamin D preparations
 - > Retinoids
- i) Use within 7 days prior to baseline of
 - Systemic antihistamines (Subjects on a stable and continued dose of systemic antihistamines may be enrolled at the investigator's discretion when the investigator considers that such will not affect the efficacy or safety evaluations of the study.)
 - > Topical antibiotics
 - > Topical corticosteroids
 - > Other topical drug products
 - > Probiotics
- j) Use within 24 hours prior to baseline of any topical product (e.g., sunscreens, lotions, creams) in the areas to be treated, except for bland emollient (e.g., Cetaphil® Lotion).

CONFIDENTIAL

Version 2.0 Dated 14 Oct 2016

k) Known allergy or hypersensitivity to pimecrolimus or any other component of the test product or RLD

- 1) Not willing to minimize or avoid natural and artificial sunlight exposure during treatment

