12.8 Appendix VII: US Reference Listed Drug Package Insert

ELIDEL- pimecrolimus cream Valeant Pharmaceuticals North America LLC

HIGHLIGHTS OF PRESCRIBING INFORMATION

These highlights do not include all the information needed to use ELIDEL® safely and effectively. See full prescribing information for ELIDEL®.

ELIDEL® (pimecrolimus) Cream, 1% for topical use Initial U.S. Approval: 2001

WARNING: LONG-TERM SAFETY OF TOPICAL CALCINEURIN INHIBITORS HAS NOT BEEN ESTABLISHED

See full prescribing information for complete boxed warning.

Although a causal relationship has not been established, rare cases of malignancy (e.g., skin and lymphoma) have been reported in patients treated with topical calcineurin inhibitors, including ELIDEL Cream, 1%. (5.1)

Therefore:

- Continuous long-term use of topical calcineurin inhibitors, including ELIDEL Cream, 1%, in any age group should be avoided, and application limited to areas of involvement with atopic dermatitis. (2,
- ELIDEL Cream, 1% is not indicated for use in children less than 2 years of age. (1, 5.1, 8.4)

------ INDICATIONS AND USAGE ------

ELIDEL Cream, 1% is a calcineurin inhibitor immunosuppressant indicated as second-line therapy for the short-term and non-continuous chronic treatment of mild to moderate atopic dermatitis in non-immunocompromised adults and children 2 years of age and older, who have failed to respond adequately to other topical prescription treatments, or when those treatments are not advisable. (1)

-----DOSAGE AND ADMINISTRATION ------------

- Apply a thin layer of ELIDEL Cream, 1% to the affected skin twice daily. (2)
- If signs and symptoms persist beyond 6 weeks, patients should be re-examined. (2)
- · Continuous long-term use of ELIDEL Cream, 1% should be avoided. (2)
- Avoid use with occlusive dressings. (2)

----- DO SAGE FORMS AND STRENGTHS -------

Cream, 1%. (3)

------CONTRAINDICATIONS -------

ELIDEL® (pimecrolimus) Cream 1% is contraindicated in individuals with a history of hypersensitivity to pimecrolimus or any of the components of the cream. (4, 6.2) ------ WARNINGS AND PRECAUTIONS ------

· Should not be used in immunocompromised adults and children, including patients on systemic immunosuppressive

- Avoid treatment on malignant or pre-malignant skin conditions, as these can present as dermatitis. (5.2)
- Should not be used in patients with Netherton's Syndrome or skin diseases with a potential for increased systemic absorption. (5.2)

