 care practices. If you use moisturizers, apply them after ELIDEL Cream, 1%.
- Call your doctor if your symptoms get worse with ELIDEL Cream, 1% or your symptoms do not improve after 6 weeks of treatment.

What should I avoid while using ELIDEL Cream, 1%?

- You should not use sun lamps, tanning beds, or get treatment with ultraviolet light therapy during treatment with ELIDEL Cream, 1%.
- Limit your time in the sun during treatment with ELIDEL Cream, 1% even when the medicine is not
 on your skin. If you need to be outdoors after applying ELIDEL Cream, 1%, wear loose fitting
 clothing that protects the treated area from the sun. Ask your doctor what other types of protection
 from the sun you should use. It is not known how ELIDEL Cream, 1% may affect your skin with
 exposure to ultraviolet light.
- Do not cover the skin being treated with bandages, dressings or wraps. You can wear normal clothing.
- ELIDEL Cream, 1% is for use on the skin only. Do not get ELIDEL Cream, 1% in your eyes, nose, mouth, vagina, or rectum (mucous membranes). If you get ELIDEL Cream, 1% in any of these areas, burning or irritation can happen. Wipe off any ELIDEL Cream, 1% from the affected area and then rinse the area well with cold water.
- Do not swallow ELIDEL Cream, 1%. If you do, call your doctor.
- · Avoid using ELIDEL Cream, 1% on skin areas that have cancers or pre-cancers.

What are the possible side effects of ELIDEL Cream, 1%?

ELIDEL Cream, 1% may cause serious side effects.

- See "What is the most important information I should know about ELIDEL Cream, 1%?"
- The most common side effect at the skin application site is burning or a feeling of warmth. These
 side effects are usually mild or moderate, happen during the first few days of treatment, and usually
 clear up in a few days.

Other common side effects include:

- headache
- · common cold or stuffy nose, sore throat
- cough
- flu (influenza)
- fever
- viral infection. Some people may get viral skin infections (like cold sores, chicken pox, shingles, or warts) or swollen lymph nodes (glands).

Tell your doctor if you get a skin infection or if you have any side effect (for example, swollen glands) that bothers you or that does not go away.

These are not all the possible side effects with ELIDEL Cream, 1%. Ask your doctor or pharmacist for more information.

Call your doctor for medical advice about side effects. You may report side effects to FDA at [name].

How should I store ELIDEL Cream, 1%?

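### The eligibility rules bar malignancy but do not expressly bar a recognised pre-malignant lesion inside an area to be treated, which the appended label says to avoid

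*Protocol*

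**What the plan says.** The label appended to the protocol gives the precaution three times:

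- Label section 5.2: "The use of ELIDEL Cream, 1% should be avoided on malignant or pre-malignant skin conditions".
- Label Highlights: "Avoid treatment on malignant or pre-malignant skin conditions, as these can present as dermatitis".
- Medication Guide: "Avoid using ELIDEL Cream, 1% on skin areas that have cancers or pre-cancers".

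The protocol's eligibility text covers malignancy only. Exclusion (e), in the synopsis and in 4.1.2, begins "History or presence of Netherton's Syndrome, immunological deficiencies or diseases, HIV, diabetes, malignancy" and goes on to serious infection and to renal and hepatic disease. Section 3.1.1.11 requires a full-body skin examination for dermatologic malignancies and adds: "If the subject does have a dermatologic malignancy, they should not be enrolled".

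On who is treated and where, section 3.1.2.12 says "Subjects fulfilling inclusion and exclusion criteria will receive study product from the next available sequential randomized kit". The synopsis says "A thin layer is to be applied to all affected skin areas twice daily", and 3.1.2.13 tells subjects to "apply a thin layer to the affected areas twice daily for 2 weeks (14 days". Section 1 (About Study Drug, Dosage & Administration) restricts use of the cream to skin involved with AD.

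**The concern.** The label pairs malignant with pre-malignant skin, but the eligibility rules name only the first. A subject with a lesion the examiner recognises as pre-malignant, sitting within a patch of AD, can satisfy every written criterion, receive a kit, and be told to treat that patch.

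The matter at stake is individual safety and consistency between sites. Two investigators finding the same lesion could decide differently, each within the protocol. It is not a question about the equivalence or superiority result.

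**Working it through.** The plan states no figure on this point, so the check is a comparison of texts, followed by an illustrative range.

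**1. Label section 5.2 against the eligibility rules**

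| Skin condition named in label 5.2 | Where the protocol names it |
|---|---|
| Malignant | Exclusion (e); 3.1.1.11 |
| Pre-malignant | Not named |
| Netherton's Syndrome | Exclusion (e) |
| Generalized erythroderma | Exclusion (d), as erythroderma |

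The table leaves out the label's open class of other skin diseases with possible raised absorption. It also treats malignant and pre-malignant as separate items, although the label puts them in one phrase. It shows which word was not carried over; it is not a measure of importance.

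The next precaution, label 5.3 on infection at treatment sites, did become a rule: exclusion (b), which is already limited to treatment areas.

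**2. Do other exclusions reach the lesion?**

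- (c) covers sunburn, extensive scarring and pigmented lesions in a treatment area, and only where they would interfere with evaluation.
- (d) covers confounding skin conditions. The list is open, but none of its examples is pre-malignant.
- (f) covers concurrent disease likely to interfere with treatment or evaluation.

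Each allows exclusion on the investigator's judgement; none requires it.

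**3. Does the application-site limit reach it?** Section 1 keeps the cream on AD skin. That deals with a recognised lesion on skin free of AD. It does not deal with one inside an AD area, because that area is still to be treated.

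**4. Would the analysis show such a subject?** The baseline variables in SAP 10.3 record dermatologic malignancy as yes or no, so that summary would not. Listing 16.2.4.2.2 has a column for dermatological examinations and might.

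**5. Illustrative size.** Protocol 9.1 gives 648 subjects, of whom 216 + 216 = 432 receive pimecrolimus. The documents give no prevalence. Assume, for illustration only, that 0% to 1% of otherwise eligible subjects have such a lesion:

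- Subjects enrolled with one: 648 × 0.01 = 6.5 at most, so 0 to about 6.
- On pimecrolimus: 6.48 × 432/648 = 4.3 at most, so 0 to about 4.
- Extra subjects to screen if they are excluded: 648/0.99 − 648 = 6.5 at most, so 0 to about 7.

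The upper ends come entirely from the assumed 1%.

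**The case against.** The strongest reply is that the label restricts where the cream goes, not who may use it, and that section 1 already confines it to AD skin. A lesion recognised as pre-malignant is not AD. In addition, exclusion (d) is open-ended, and the Highlights explain the precaution by saying such conditions can look like dermatitis, which is close to what (d) means by confounding. Section 4.2 lets the investigator withdraw a subject in the subject's best interest, and the label is bound into the protocol. Its only example in 5.2, cutaneous T-cell lymphoma, is a malignancy and so already barred. The new wording would itself rest on clinical judgement.

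Much of this stands, and it reduces the gap to a recognised lesion within an AD area. There, the routes to exclusion are optional and the site limit does not separate the lesion from the surrounding AD.

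Two further points also stand. A lesion mistaken for AD would escape the proposed wording as well. And the text of Appendix V, the patient instructions reviewed at dispensing, was not available for this review; it may carry a warning about such skin, though that would not alter eligibility.

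A reader might infer from the instruction to treat all affected areas that the protocol directs cream onto any pre-malignant lesion. The documents do not support that, because of the limit in section 1. Nor do they support reading this as a breach of a contraindication: label section 4 lists hypersensitivity only.

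**Conclusion.** The point holds in a narrow form. Exclusion (e) and 3.1.1.11 bar malignancy and do not expressly bar a recognised pre-malignant lesion within an area to be treated, although the appended label says not to apply the cream there.

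The weight is small. The label text is a precaution, treatment lasts 14 days, and an investigator may well exclude the subject anyway. The number affected is unknown and could be zero. Nothing here changes power, sample size, the equivalence analysis or the superiority tests. It is a cheap improvement of the lowest grade, with moderate confidence. The conclusion assumes that malignancy in exclusion (e) is read as the label uses it, distinct from pre-malignant.

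**What to change.** Add *clinically recognised pre-malignant skin condition in any treatment area at baseline* to exclusion (e) in 4.1.2 and in the synopsis, and to the enrolment sentence in 3.1.1.11. The limit to treatment areas at baseline follows exclusions (b) and (c), and restricting it to recognised lesions keeps it to what an examiner can act on.

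The change is a few words in three places and can travel with the next amendment. The full-body skin examination is already done at screening, so no procedure is added.

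There are two costs. One is a few possible screen failures, 0 to about 7 under the assumed range. The other arises if a violation is found after randomization: 4.2 calls for discontinuation, and 9.2.1.2 and 9.2.1.3 remove the subject from the mITT and PP populations. That should be rare. One such subject is 1/205 = 0.5% of a planned mITT group, or 1/184 = 0.5% of a planned PP group.
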